	Halwa 20 g/kg.feed 3 feeds per day	144	3.0
	Khichuri 20 g/kg.feed 3 feeds per day	87	1.8
	Total	271	5.8

* There is a gap in feeding at 4 a.m.

Diets 1, 2, 3 and 4 are provided on days 1, 2, 3 and 4 respectively of the nutritional rehabilitation phase. These diets ensure 2 hourly feeds with milk suji at least for the first 4-5 days of nutritional rehabilitation. Diet 5 is started only when the child achieves an intake of 225 kcal/kg per day, and is continued till the end of stay in the NRU. Most of the calorie and protein in diet 5 are derived from halwa and khichuri, the number of milk feeds being only four per day. Thereafter, halwa and khichuri can easily be continued at home. The child is given plain water in between the feeds. The amount of each feed offered and actually taken is recorded on a feeding chart.

Children are discharged from the NRU once they have achieved an energy intake of >250 kcal/kg per day (with 5 g/kg per day of protein intake), have attained a WL z-score >-2, are edema free, and have a good general condition.

Antibiotic therapy

In children without signs or symptoms of infection other than those of diarrhea, therapy is initiated with ampicillin 100 mg/kg per day q6 hourly and gentamicin 5 mg/kg per day q12 hourly i.m. or i.v. (17), and continued for 7 days. If no clinical or other evidence of septicemia is present after 48 hours, ampicillin is discontinued and

amoxicillin 100 mg/kg per day q8 hourly is given orally for 5 additional days. Children with pneumonia are treated with chloramphenicol 100 mg/kg per day q6 hourly i.v. for 24 hours and then orally for a total of 7 days (27). Children on treatment with chloramphenicol will not be enrolled because the antibiotic also affects anaerobic flora. Children with pneumonia being treated with ceftriaxone, which has no impact on anaerobic bacteria, will be enrolled subject to fulfilment of other conditions.

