Hypoglycaemia (blood glucose <3 mmol/L) is managed with 50 mL of 10% glucose administered orally or through a NG tube. If a hypoglycaemic child is unconscious or convulsing, 25% glucose is administered i.v., 2 mL/kg, followed by oral glucose. Children with severe acidosis (serum CO₂ <6 mmol/L) are given sodium bicarbonate 1 mL/kg i.v. slowly. Normal saline or solution A is infused 20 mL/kg over one hour in case of septic shock and the infusion is repeated once if necessary. Children with hypokalemia receive oral potassium, 5 mmol/kg per day. Children with a serum K⁺ <2 mmol/L requiring parenteral hydration are infused with an i.v. fluid containing K⁺ up to 40 mmol/L. If the haematocrit is <15%, 10 mL/kg of packed red cells or whole blood is transfused over 3 hours. Hypothermia, abdominal distension, congestive heart failure, and weeping skin lesions are managed according to WHO guidelines (18).

Follow up

Upon discharge from the NRU, children are advised to attend the nutritional follow up clinic (NFU) at intervals of one week, two weeks, and then one month until achievement of WL z-score >-1, which is usually possible in 6-8 months. A health worker discusses the overall condition of the child, the change in weight and the child's diet with the mother during each follow-up visit. Intercurrent illnesses are treated. Preparation of khichuri and halwa is demonstrated, health and nutrition education provided to the mothers. Health workers visit the homes of defaulting children.

Outcome variables

The two major outcome variables that will be compared between the study and placebo groups are:

1. Rate of weight gain, calculated from lowest and discharge weights in terms of g/kg body weight per day.
2. Days to achieve edema-free weight-for-length (WL) z-score >-2 according to the US National Centre for Health Statistics reference.

Sample size

An analysis of 66 severely malnourished children (WL <70%) recovering from diarrhea who received nutritional rehabilitation in our NRU showed that their weight gain was 11.4 ± 6.0 g/kg per day, and the time to achieve 80% WL was 15.5 ± 9.4 days. Assuming worthwhile differences of 3 g/kg per day for weight gain and 5 days for time to achieve 80% WL (WL z-score >-2) with metronidazole treatment, sample sizes of 63 and 56 children respectively in each group are calculated using the formula:

$$\frac{2(SD)^2}{(WD)^2} \cdot \text{factor for } \alpha, \beta$$

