The investigators will perform data entry, data cleaning and analysis themselves. Data will be entered into a personal computer simultaneously with the progress of each subject. SPSS Windows software will be used to analyse data. The software Epi info 6.0 will be used to calculate anthropometric indices. The outcome variables will be compared both within (if applicable) and between groups from enrollment to discharge. For normally distributed quantitative variables, means will be compared by Student's t-test. Variables not normally distributed will be log transformed before analysis. Categorical variables will be compared by Chi-square, multiple or logistic regression will be performed to minimise bias if required.

The code will be opened only after a preliminary analysis has been performed using dummy group names for the study and control groups, provided by the code holder, e.g., groups A and B. If an enrolled child develops a condition requiring metronidazole therapy, i.e., toxic colitis or peritonitis, then his/her code may be opened. Data from all randomized children will be included in the analysis. As all children will be enrolled with an intention to treat, data of children withdrawn from the study but who continue to remain and receive treatment in the hospital will also be included in the analysis.

Ethical Assurance for Protection of Human Rights

Describe in the space provided the justifications for conducting this research in human subjects. If the study needs observations on sick individuals, provide sufficient reasons for using them. Indicate how subject's rights are protected and if there is any benefit or risk to each subject of the study.

The study will test the hypothesis that use of the medicine, metronidazole, will improve the outcome of acute phase treatment and nutritional rehabilitation of severely malnourished children recovering from diarrhea and other acute illness(es). Metronidazole is not a new medication, and its use is expected to eliminate small intestinal bacterial overgrowth as well reduce the morbidity and mortality from life-threatening anaerobic infections in children with severe malnutrition. This study aims at improving the outcome of treatment of severely malnourished children who are brought to the hospital in an acutely ill condition.

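### Days to recovery (outcome 2) is a time to event, but the planned t-test or log t-test has no value for children who die or leave before reaching the target

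*Protocol*

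**What the plan says.** The Outcome variables section (and Specific Aims) lists as the second major outcome: "Days to achieve edema-free weight-for-length (WL) z-score >-2 according to the US National Centre for Health Statistics reference".

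Data Analysis does not name a test outcome by outcome. It gives a general rule: "For normally distributed quantitative variables, means will be compared by Student's t-test. Variables not normally distributed will be log transformed before analysis". The only other methods named are in the next sentence: "Categorical variables will be compared by Chi-square, multiple or logistic regression will be performed to minimise bias if required". No method for censored times appears. The Sample size section treats the outcome in the same way, as a difference of two means, from data in which "the time to achieve 80% WL was 15.5 ± 9.4 days".

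On who is analysed, Data Analysis says "Data from all randomized children will be included in the analysis" and adds that "data of children withdrawn from the study but who continue to remain and receive treatment in the hospital will also be included in the analysis". The window is also set there: "The outcome variables will be compared both within (if applicable) and between groups from enrollment to discharge". Nothing says what is entered for a child who dies or goes home before the target.

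Under Diet therapy, discharge from the NRU requires, besides an energy and protein intake, that children "have attained a WL z-score >-2, are edema free, and have a good general condition".

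**The concern.** Outcome 2 is observed only in children who reach the target. For the others, the number of days is not skewed or noisy; it does not exist. A log transformation deals with skew and does nothing for a missing endpoint. The stated tests therefore compare the children who recovered in one arm with the children who recovered in the other, and the randomized comparison is lost for this outcome.

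This matters most if exits differ by arm, and the protocol gives grounds to expect that. Its third hypothesis is that the drug reduces morbidity, including sepsis, and Ethical Assurance expects lower mortality from anaerobic infection. If so, more placebo children leave the comparison early. A long recovery is more exposed to early exit than a short one, so the placebo mean is shortened more and the comparison tilts against the drug. The opposite imbalance tilts it in the drug's favour.

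**Working it through.** **1. The plan's own figures.** The formula is n per group = 2·SD²/WD² × (1.960 + 0.842)², and the last factor is 7.849.
- Weight gain: 2 × 6.0²/3² × 7.849 = 62.8, so 63 (stated 63).
- Days to target: 2 × 9.4²/5² × 7.849 = 55.5, so 56 (stated 56).
- Dropout: 63/0.9 = 70 (stated 70).

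All reproduce, so the sizing arithmetic is not at fault. It does confirm that outcome 2 is meant to be compared as a mean.

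**2. Which children lack a value.**

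| Child | Days to target | t-test or log t-test |
|---|---|---|
| Discharged under the stated criteria | Observed | Included |
| Withdrawn from study, stays in hospital to the target | Observed | Included |
| Dies before the target | None | Omitted |
| Taken home before the target | None | Omitted |

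The protocol expects some in the last group. It allows 10% dropouts (refusal, or tuberculosis diagnosed later) and lets parents withdraw at any time. Its dropout allowance does not mention deaths.

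**3. Size of the effect.** Inputs from the protocol: mean 15.5, SD 9.4, 70 per arm. Assumptions: lognormal recovery times, exponential exits independent of recovery time, and the exit rates themselves. There were 3,000 to 4,000 simulated trials per scenario. The t-test and log t-test use completers only. The log-rank test uses all 70 per arm, with exits censored.

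No true effect:

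| Exits, metronidazole v placebo | Spurious difference (days) | t-test rejects | log t-test rejects | log-rank rejects |
|---|---|---|---|---|
| 10% v 10% | about 0 | about 5% | 5% | about 5% |
| 10% v 20% | 0.6 | 6.5-7% | 6-7% | 5-6% |
| 7% v 20% | 0.8 | 7% | 7% | about 5% |
| 5% v 32% | 1.6 | 15% | 15% | 5% |

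In the unequal rows the spurious difference makes metronidazole look slower.

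True 5-day benefit (means 10.5 v 15.5, SD scaled with the mean): with about 4% v 32% exits, completers show only about 3.3 days. Power is 71% (t), 80% (log t) and 94% (log-rank).

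**4. When exits depend on recovery time.** Suppose there is no true effect, but the slowest 5% in one arm and the slowest 15% in the other never have a recovery date. Completer means are then about 14.0 and 12.5 days, a spurious 1.6 days or about one third of the 5-day worthwhile difference. With the lost children censored at a uniform time before the cut-off (a further assumption), rejection is about 30% (t), 18% (log t) and 24% (log-rank). Censoring does not cure this case.

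**The case against.** The strongest reply is that the gap is narrow and may be harmless. Discharge is tied to the target, so every child who completes the stay has a value. The only loss figure planned is 10%, not split by arm, and at 10% in both arms the t-test keeps its error rate. An imbalance of 7% v 20% adds only about two percentage points. Skew is already covered by the log rule, and weight gain, not days, sets the sample size. All of this stands. It lowers the weight of the point but does not remove it: the stated tests still cannot honour the stated analysis set, and the drug's expected benefit is itself a reason for unequal exits.

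Three stronger readings are tempting and not supported:
- **That the day of leaving will be entered as the day of recovery**, scoring a death as a fast recovery. The protocol contains no such rule, so no size is given for it.
- **That the worldwide mortality of 20-30% in the Background is the loss to expect here.** It is background, not a rate for this trial.
- **That a log-rank test solves the problem in all cases.** Step 4 shows that it does not when slow children are lost preferentially.

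Nor is this a detail left to a separate analysis plan. The protocol states a method, and that method does not fit this outcome.

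**Conclusion.** The point holds, as one that should be fixed. For outcome 2 the prescribed tests must omit children who die or leave before the target, which contradicts the commitment to analyse everyone randomized.

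With equal exits the cost is mainly lost information and a non-randomized comparison; type I error stays near 5%. With unequal exits the bias is about 0.8 days at 7% v 20% and about 1.6 days at 5% v 32%, with rejection of about 7% and 15% under no effect. These sizes rest on the assumed lognormal shape and assumed exit rates. The log-rank result of about 5% rests also on exits being independent of recovery time. Neither the sample size nor the weight-gain outcome is questioned here.

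**What to change.** In Data Analysis, except outcome 2 from the t-test/log rule and state:

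- All randomized children are analysed, with days counted from randomization.
- Recovery is shown by Kaplan-Meier or cumulative-incidence curves. Arms are compared by a log-rank test with a Cox hazard ratio, both stratified by edema as the randomization is.
- Departures are censored on the last hospital day.
- Deaths count as never recovered (competing event) in the cumulative-incidence analysis. The cause-specific log-rank/Cox result, which censors deaths, is reported as a separate estimate. These are two different analyses, so say in advance which one leads.
- Median or restricted mean days are reported, with the horizon fixed in advance, so that the result can be read against the 5-day difference.
- A sensitivity analysis counts departures as not recovered, with a statement that censoring does not remove bias if slow children are taken home preferentially.

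Cost: a change of wording before the code is opened, somewhat more analysis work, and no extra children. The date and reason of every exit must be on file. The main estimate relies on departures being non-informative, which is why the sensitivity analysis is needed. Little power is given up: in the simulation with a 5-day benefit and no exits it was 95% for log-rank, 96% for the t-test and 98% for the log t-test.

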A randomized double-blind trial has been designed to evaluate the efficacy of metronidazole in improving nutritional rehabilitation of severely malnourished children recovering from diarrhea by treating small intestinal anaerobic infection. Severely malnourished children of either sex (weight-for-length z-score <-3 according to the US National Centre for Health Statistics reference, or with edema), aged 6-60 months, with diarrhea and other associated illnesses including pneumonia will be enrolled into the study. Seventy eligible children will be randomized to receive metronidazole, and 70 to receive a placebo. The randomization will be stratified so that an equal proportion of children with edema are enrolled into each of the two groups. The children will be treated in the in-patient facility of the Clinical Research and Service Centre of the ICDDR,B according to routinely used standardized protocols for the acute and the nutritional rehabilitation phases of management. In addition, they will receive either metronidazole 30 mg/kg per day q8 hourly orally, or a placebo, for 7 days. All mothers will receive health and nutrition education, and hands-on training on preparation of nutritious diets from locally available, inexpensive foods. The metronidazole and placebo groups will be compared in terms of anthropometric indices on admission and upon discharge, rate of weight gain, and time to recovery (achieving weight-for-length z-score >-2). The variables will be compared within (if applicable) and between groups from enrollment to discharge. If metronidazole treatment (which is inexpensive) along with nutritional therapy is found to increase weight gain and reduce the period of stay in the NRU, then it will be possible to reduce the cost of treating severely malnourished children.

KEY PERSONNEL (List names of all investigators including PI and their respective specialties)

Name	Professional discipline/ specialty	Role in the project
1. [name]	Pediatrician and Nutritionist	PI
2. [name]	Pediatric Gastroenterologist & Nutritionist	Co-PI
3. [name] [name]	Internist	Co-Investigator
4. [name]. [name]	Internist	Co-Investigator
4. [name]. [name]	Internist	Co-Investigator
5. [name]	Internist	Co-Investigator

DESCRIPTION OF THE RESEARCH PROJECT

Hypothesis to be tested:

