Describe in detail the methods and procedures that will be used to accomplish the objectives and specific aims of the project. Discuss the alternative methods that are available and justify the use of the method proposed in the study. Justify the scientific validity of the methodological approach (biomedical, social, or environmental) as an investigation tool to achieve the specific aims. Discuss the limitations and difficulties of the proposed procedures and sufficiently justify the use of them. Discuss the ethical issues related to biomedical and social research for employing special procedures, such as invasive procedures in sick children, use of isotopes or any other hazardous materials, or social questionnaires relating to individual privacy. Point out safety procedures to be observed for protection of individuals during any situations or materials that may be injurious to human health. The methodology section should be sufficiently descriptive to allow the reviewers to make valid and unambiguous assessment of the project. (DO NOT EXCEED TEN PAGES, USE CONTINUATION SHEETS).

Design

This will be a randomized, double-blind, placebo-controlled trial stratified by type of malnutrition (edematous or non-edematous). Eligible children will be assigned to one of the two treatment groups according to the random numbers table, using permuted blocks of variable lengths. In order to ensure equal distribution of edematous and non-edematous children in the two treatment groups, separate tables of random numbers will be used. A trained and responsible person not involved with the study will prepare the randomization lists and preserve the master code. The study drug and the placebo, in identical amber-colored bottles, will be procured from a pharmaceutical industry experienced in the preparation of drugs for clinical trials. The placebo will be made similar in colour to the study drug. The bottles will be stored in and dispensed from the hospital pharmacy.

Methods

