where, SD is the standard deviation, WD is the worthwhile difference, power is 80%, and type I error is 0.05. Taking the greater of the two calculated sample sizes and allowing for 10% dropouts (refusal to continue, or later diagnosed to have tuberculosis), there will be 70 children in each group.

Facilities Available

Describe the availability of physical facilities at the place where the study will be carried out. For clinical and laboratory-based studies, indicate the provision of hospital and other types of patient's care facilities and adequate laboratory support. Point out the laboratory facilities and major equipments that will be required for the study. For field studies, describe the field area including its size, population, and means of communications. (TYPE WITHIN THE PROVIDED SPACE).

Severely malnourished children will be treated for the acute phase of malnutrition in the general ward or special care unit of the CRSC of ICDDR,B. This will follow the routine practice in the CRSC. The children will be transferred to the NRU of the CRSC as soon as the acute phase treatment is complete and the children are fit for the nutritional rehabilitation phase. Treatment will be provided by a team consisting of study investigators and CRSC staff members. Existing diagnostic laboratory and radiology facilities of the Centre will be utilized.

Data Analysis

Describe plans for data analysis. Indicate whether data will be analyzed by the investigators themselves or by other professionals. Specify what statistical softwares packages will be used and if the study is blinded, when the code will be opened. For clinical trials, indicate if interim data analysis will be required to monitor further progress of the study. (TYPE WITHIN THE PROVIDED SPACE).

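### Randomisation is stratified by edema, but the fixed comparison is an unadjusted t-test with regression only if required, so some precision may be lost and the choice to adjust is left open

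*Protocol*

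**What the plan says.** - **Design (Research Design and Methods):** "This will be a randomized, double-blind, placebo-controlled trial stratified by type of malnutrition (edematous or non-edematous". Separate random number tables, with permuted blocks, are used for the two types.
- **Project summary:** "The metronidazole and placebo groups will be compared in terms of anthropometric indices on admission and upon discharge". Anthropometry is therefore available at admission. Weight-for-length is also an entry criterion.
- **Data Analysis:** means of normally distributed variables are compared by Student's t-test, and other variables are log transformed first. The only mention of adjustment is "multiple or logistic regression will be performed to minimise bias if required". Neither edema nor admission weight-for-length is named, and nothing says what would make regression necessary.
- **Data Analysis, blinding:** the investigators analyse the data themselves. The code is opened only after a preliminary analysis under dummy group names.
- **Sample size:** "their weight gain was 11.4 ± 6.0 g/kg per day" and "the time to achieve 80% WL was 15.5 ± 9.4 days" are the planning values, and "power is 80%, and type I error is 0.05".

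**The concern.** Stratified allocation makes the arms nearly equal in their share of edematous children. The treatment difference then carries almost no between-stratum variation. A plain t-test still counts that variation in its standard error. If edema predicts outcome, the standard error is too large, the interval too wide and the true type I error below 5%.

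Admission weight-for-length is a different case. It is not balanced by design, so the unadjusted interval has its proper coverage. Leaving the covariate out costs only precision, and only as far as it predicts the outcome.

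The protocol gives some reason to expect prognostic value. Recovery is defined as edema-free with a weight-for-length z-score above -2, so edema and starting z-score both bear on the days needed.

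The conditional wording is a second weakness. In a randomised comparison, baseline adjustment mainly serves precision and agreement with the design, so it should not wait for an observed imbalance. As written, whether to adjust, and for what, can be settled after the A-versus-B result has been seen. That leaves two candidate results for each outcome.

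**Working it through.** **Inputs from the Sample size section.** SD 6.0 g/kg per day and 9.4 days. Worthwhile differences: "Assuming worthwhile differences of 3 g/kg per day for weight gain and 5 days for time to achieve 80% WL". Power is 80% and alpha 0.05. Sidedness is not stated.

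**Step 1: the plan's own figures.** n = 2·SD²/WD² × (1.960 + 0.842)², where the squared factor is 7.849.
- Weight gain: 2 × 36/9 × 7.849 = 62.8, so 63.
- Days: 2 × 88.36/25 × 7.849 = 55.5, so 56.
- Dropout: 63/0.90 = 70.

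This matches "sample sizes of 63 and 56 children respectively in each group are calculated" and the 70 per group. One-sided testing would give 50 and 44, so the plan is two-sided. The sample size uses unadjusted SDs and agrees with an unadjusted test.

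**Step 2: adjusted precision.** R² is the share of outcome variance explained by the baseline terms. The protocol does not give it, so 0 to 0.30 is assumed. The residual SD is SD × f, with f = √(1 − R²). With 63 per group, the unadjusted standard error for weight gain is 6 × √(2/63) = 1.069. Power is Φ(3/(1.069·f) − 1.96) and the 95% half-width is 1.96 × 1.069 × f. The days outcome is treated likewise, with SD 9.4 and difference 5.

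**Step 3: true size of the t-test if edema alone explains R².** The estimate varies with standard error 1.069·f but is judged against 1.069, so the size is 2 × [1 − Φ(1.96/f)].

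| R² (assumed) | f | Power, weight gain | Half-width, g/kg per day | Power, days | Half-width, days | True size of t-test if edema alone explains R² |
|---|---|---|---|---|---|---|
| 0 | 1.000 | 80.1% | 2.10 | 84.7% | 3.28 | 5.0% |
| 0.05 | 0.975 | 82.1% | 2.04 | 86.5% | 3.20 | 4.4% |
| 0.10 | 0.949 | 84.1% | 1.99 | 88.2% | 3.11 | 3.9% |
| 0.20 | 0.894 | 88.1% | 1.87 | 91.6% | 2.94 | 2.8% |
| 0.30 | 0.837 | 91.8% | 1.75 | 94.6% | 2.75 | 1.9% |

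These use the normal approximation. The noncentral t gives 79.5%, 83.5%, 87.6% and 91.4% for weight gain at R² of 0, 0.10, 0.20 and 0.30.

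**Step 4: simulation.** Edema-stratified allocation of 126 children, 40% edematous (assumed), 8,000 runs per setting.
- With no treatment effect, the t-test rejected in 4.3%, 3.5%, 2.9% and 1.9% of runs when edema explained 5%, 10%, 20% and 30%.
- With a true difference of 3 g/kg per day, power for the t-test against the model with edema was 81% v 84% (R² 0.10), 82% v 88% (0.20) and 84% v 92% (0.30). When edema is the source of R², the t-test itself rises slightly above 80%, because the design already removes some variation. The gain is then somewhat smaller than the distance from 80% in the table.
- At R² = 0, power was 80.4% for the t-test, 80.5% with edema, and 80.0% with edema and a baseline covariate. A useless covariate costs almost nothing.

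**The case against.** The strongest reply is that nothing here is invalid. The trial is sized on unadjusted SDs and analysed by an unadjusted test, and the two agree. The t-test is valid or conservative. Choice of covariates is commonly left to an SAP, and every gain rests on an R² that the protocol does not give. Most of this stands. It makes the point an improvement and leaves its size conditional. It does not dispose of the point, because the protocol itself fixes the unadjusted test and makes regression conditional.

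There are also reasons to doubt a large edema effect on rate of weight gain. Rate runs from the lowest weight, which removes much of the effect of edema loss, and the nutritional rehabilitation unit's feeding schedule is the same for all children. The acute-phase diets do differ, but they group marasmic kwashiorkor with marasmus, so they do not clearly follow the edema strata. Small values of R² must therefore stay in the range.

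The dummy group names are a partial safeguard: they hide the direction of the difference but not its size or p value.

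Three stronger readings are tempting and are not supported:
- *Unadjusted intervals are too wide for both factors.* This holds only for edema.
- *The 5% test really runs at about 2.4%.* That needs R² = 0.25, for example equal-sized strata differing by 6 g/kg per day. Such a gap is a full SD and twice the worthwhile difference, and the protocol documents neither condition.
- *Starting weight-for-length strongly drives the result.* At 11.4 g/kg per day, going from 60% to 80% takes (20/60 × 1000)/11.4 = 29 days, and from 70% takes (10/70 × 1000)/11.4 = 12.5. This concerns days to target and says nothing about rate. It also assumes one constant rate and an arbitrary start at 60%.

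**Conclusion.** The point holds as a low-cost improvement. The design stratifies by edema and measures weight-for-length at admission, while the stated analysis uses neither and leaves adjustment open. For weight gain with 63 evaluable per group, adjusting takes power from about 80% to about 82%, 84%, 88% and 91-92% at assumed R² of 0.05, 0.10, 0.20 and 0.30. Intervals narrow by about 2.5%, 5%, 11% and 16%. At R² = 0 there is no gain. If edema alone supplied that R², the t-test's true size would be about 4.4%, 3.9%, 2.8% and 1.9%.

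A reader might infer that the t-test is biased, that it raises the false-positive rate, or that the trial is too small. None of these follows. Ignoring a balanced stratum lowers the type I error, and 63, 56 and 70 reproduce exactly. The open choice between an unadjusted and an adjusted result is a separate weakness, and its size is not estimated here.

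**What to change.** Before the preliminary analysis under dummy names, state as the main analysis of each quantitative outcome (on the log scale if needed) a linear model with treatment, edema stratum and admission weight-for-length z-score. Keep the unadjusted t-test as a supporting analysis and delete *if required*.

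Define the admission z-score: which weight, and when it is taken. In edematous children it includes edema fluid and partly overlaps the stratum, so its added value there may be small. The protocol does not say that a rehydrated z-score is recorded, so the model should not assume one.

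If a time-to-event method is used for days to target, it should carry the same stratum and covariate. Whether to use such a method is a separate question.

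The cost is about two sentences and up to two degrees of freedom, with no new measurements and no change in sample size.

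### The code may be opened after only a preliminary analysis, so data cleaning and the final analysis may be completed with the metronidazole arm known

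*Protocol*

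**What the plan says.** All but two of the relevant statements are in the protocol's Data Analysis section.

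- **When the code opens.** "The code will be opened only after a preliminary analysis has been performed using dummy group names for the study and control groups". The dummy names are "provided by the code holder, e.g., groups A and B".
- **Who handles the data.** "The investigators will perform data entry, data cleaning and analysis themselves".
- **What is left to judgement.** "Variables not normally distributed will be log transformed before analysis", with no criterion for normality. Also, "multiple or logistic regression will be performed to minimise bias if required", with no covariates named and no trigger defined.
- **Individual openings.** "If an enrolled child develops a condition requiring metronidazole therapy, i.e., toxic colitis or peritonitis, then his/her code may be opened". The text does not say who is told.

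The other two are elsewhere. Facilities Available states: "Treatment will be provided by a team consisting of study investigators and CRSC staff members". The Design section gives the randomization lists and master code to a person outside the study.

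**The concern.** The protocol form asks when the code of a blinded study will be opened, and this protocol answers with a rule. So the concern is the rule itself, not a detail missing until a statistical analysis plan appears. Calling the masked analysis preliminary implies that another follows, and under this rule the later one may be run with the arms known.

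Three features make the timing matter here:

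1. Members of one team may treat the children, clean the data and analyse them.
2. The judgement on normality and the whole choice of covariates can still be made or revised after opening.
3. Rate of weight gain is computed from the lowest and the discharge weight, so accepting or rejecting one recorded low weight changes that child's result. Nothing requires such queries to be closed before the code is opened.

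The section on ethical assurance says that children given metronidazole are expected to do better. Masked analysis exists to protect against an expectation of that kind.

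**Working it through.** **Step 1. Trace who can know what, and when.**

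| Stage | Does the protocol require masking? |
|---|---|
| Treatment and weighing | Yes: double-blind, with a placebo and an outside code holder |
| Preliminary analysis | Yes: labels A and B |
| Completion of data cleaning | Not tied to any point before opening |
| Decision on normality, choice of covariates | Not tied to any point before opening |
| Final analysis of the two major outcomes | No: opening is allowed after the preliminary analysis |

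No other section adds a lock or requires a completed analysis before opening.

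**Step 2. The individual code opening.** There are two arms and two labels. If an analyst knows that one child received metronidazole and sees that child listed under A, then A is metronidazole and B is placebo. One child is enough. It takes three events in sequence: a qualifying complication, a decision to open the code, and disclosure to someone who also analyses.

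**Step 3. Reproduce the planning figures.** They are used only to set up the illustration below. The protocol's formula is 2·SD²/WD² times a factor. For two-sided 5% and 80% power, the factor is (1.960 + 0.842)² ≈ 7.85.

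- Weight gain: 2 × 6.0² / 3² × 7.85 = 8 × 7.85 = 62.8, so 63.
- Time to target: 2 × 9.4² / 5² × 7.85 = 7.07 × 7.85 = 55.5, so 56.
- Dropout: 63 / 0.90 = 70 per group.

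All three agree with the Sample size section.

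**Step 4. Illustrate what steered selection could do.** The protocol's inputs are 63 per arm and weight gain with mean 11.4 and SD 6.0. The covariates, their correlations with the outcome and the menu of models are assumptions. No treatment effect is simulated. The last two columns give the proportion of trials with a significant result in favour of metronidazole.

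| Setting | One fixed analysis | Most favourable analysis chosen |
|---|---|---|
| A. Lognormal outcome, one covariate (r = 0.5), log scale fixed, adjusted or not (2 models) | 2.5% | 3.6% |
| B. As A, with raw or log scale also open (4 models) | 2.5% | 4.5% |
| C. Lognormal outcome, two covariates (r = 0.3 each), raw or log (8 models) | 2.6% | 5.3% |
| D. As C, with a normal outcome | 2.7% | 6.0% |

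A and B use 20,000 simulated trials, C and D 10,000 each. For the lognormal, the log-scale variance is ln(1 + (6.0/11.4)²) = 0.245 and the log-scale mean is ln 11.4 − 0.245/2 = 2.31. The fixed analysis is unadjusted, on the log scale in A and B and on the raw scale in C and D.

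The rate in favour of metronidazole thus rises from about 2.5% to about 5%, and to 3.6% if the log rule is followed strictly. Steered data cleaning is not simulated.

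**The case against.** The strongest reply is that the wording sets only an earliest point for opening. The protocol does not say that the preliminary analysis leaves out the major outcomes or comes before cleaning, and data are to be entered as each child progresses. The code holder is outside the study, and the first analysis is masked. The transformation is not free either: the log is named, and only the judgement on normality is open. The normality criterion, the covariate list and the lock procedure are commonly left to a statistical analysis plan, which was not available here. All of this stands, and it limits the point to what the rule permits.

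Two stronger readings are tempting, and the protocol supports neither.

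- **That early opening by itself inflates the 5% error to about 10%.** In settings B to D, choosing the smallest two-sided p-value gives 9.4% to 11.7%. That choice needs no knowledge of the arm and works equally well under A and B. It measures analytic flexibility. Half of the 9.4% in setting B, 4.7%, would favour metronidazole even with masked selection. Knowing the arm lets selection be aimed in one direction; it does not create the flexibility. Having two major outcomes raises the error further, but that is a separate matter from the timing of opening.
- **That the double-blind design fails, or that one emergency opening necessarily unmasks the analysis.** Treatment and weighing stay masked under this rule. Provision for opening an individual code is ordinary in blinded trials, and the leak occurs only if the information reaches the analyst.

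**Conclusion.** The point holds in a limited form. The opening rule stops the masking of the analysis one step too early, and no other section closes the gap. The protocol allows the people who treat the children and clean the data to complete cleaning and final modelling with the arms known. It does not say that they will.

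The only figure worth giving is illustrative: about 2.5% rising to about 5% in favour of metronidazole, comparing one fixed analysis with steered selection. It rests on assumed covariates, correlations and models, and it does not isolate the effect of timing. The case for the change rests mainly on the text. The change is worth making because it is cheap, but the rule does not by itself invalidate the trial.

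**What to change.** Amend the Data Analysis section as follows.

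1. Before the code holder releases any A/B labels, clean and lock the data, and write down the normality criterion and the covariates. Moving the opening date alone would not be enough, because choices made after seeing an A-versus-B comparison can still be driven by the result.
2. Replace the preliminary analysis, as the condition for opening, with the final analysis of both major outcomes, completed and filed under A/B.
3. Label any analysis first specified after opening as post hoc.
4. Have the code holder log each individual code opening and, where team roles allow, keep it from the person who runs the A/B analysis until that analysis is filed. The clinical grounds for opening a code are not at issue here.

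The cost is a few sentences and a slightly later opening. Item 4 may mean separating treating and analysing roles within the existing team, which lists several investigators. Sample size and type I error are unchanged.
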